#### 4.2.2 Derivation rules

Not applicable.

#### 4.2.3 Presentation of results

Individual concentration data and actual blood sampling times from dose administration for PK assessments will be listed.

[figure not shown]
Descriptive statistics per treatment period and time point on concentration data will be presented in tables.

PK concentrations will be reported in ng/mL by the lab and will be converted to ug/mL for analyses.

#### 4.3 **PHARMACODYNAMICS**

PD data will be presented for the Roll-over set.

Page 42 of 84

## 4.3.1 Available data

The following PD markers will be measured in serum: total immunoglobulin G (IgG), IgG subtypes (IgG1, IgG2, IgG3, and IgG4) and anti-Dsg-1/ Dsg-3 antibodies.

## 4.3.2 Derivation rules

Changes and percent changes (compared to baseline, 1904 baseline and TPnB) will be calculated at each analysis visit. See section 2.2.2 for calculation of change and percent change from baseline and TPnB, and section 2.2.4 for the definition of analysis visits overall and by period/subperiod.

Values of anti-Dsg-1/Dsg-3 autoantibodies above or below limit of quantification will be imputed by the upper or lower limit of quantification respectively. This will be explained by a footnote in the appropriate tables. Limits of quantification are provided by the lab. For total IgG and IgG subtypes, no imputation will be applied. Listings will always show the non-imputed values.

For participants with a baseline value below the limit of quantification (BLQ), the parameter will be excluded in presentation of actual values and when computing the change from baseline and the percent change from baseline. This will be explained by a footnote in the appropriate tables.

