An innovative drug is needed for the treatment of PV and PF that has a fast onset of action (eg, early disease control [DC, defined as the absence of new lesions and the start of healing of established lesions], complete clinical remission [CR, defined as the absence of new lesions and complete healing of established lesions] within weeks), a strong prednisone sparing effect, and a favorable safety profile. The late onset of action of rituximab is well-documented in the literature: in a meta-analysis reviewing 30 studies, DC was achieved by a mean of 7 to 8 weeks and CRmin by a mean of 6.5 months.

The antecedent trial ARGX-113-1904 intends to demonstrate that efgartigimod PH20 SC with an add-on therapy of oral prednisone at low doses would be a possible treatment modality for PV and PF that could lead to early disease remission at minimal prednisone dose. This trial has a treatment period of up to 30 weeks and provides a tailored dose regimen for participants by stopping investigational medicinal product (IMP) administration upon achieving CRmin (defined as the absence of new lesions and complete healing of established lesions while the participant receives minimal prednisone therapy of \leq 10 mg/day for at least 2 months [8 weeks]). *Note: when 10 mg/day is reached in ARGX-113-1904 or ARGX-113-1905, this dose level must be maintained for 8 weeks until CRmin has been achieved*.

This trial provides extension of efgartigimod PH20 SC treatment and retreatment options for participants who have been randomized to the efgartigimod PH20 SC treatment arm in ARGX-113-1904, and the first treatment of efgartigimod PH20 SC and retreatment options for participants who had been randomized to the placebo arm in ARGX-113-1904.

At the blinded rollover from ARGX-113-1904 into ARGX-113-1905, participants may be in different clinical stages of treatment. Participants may have achieved CRmin, participants may have achieved CR without meeting the minimal therapy criterion, participants may have achieved DC or end of consolidation (EoC, the time at which no new lesions have developed for a minimum of 2 weeks and approximately 80% of lesions have healed) without having achieved CR, participants may have had treatment failure or a flare after having achieved CRmin.

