GTI	Х						Xr							Xr			
IMP self-administration training ^s	X	X	X	X	X	X	Х	X	Х	Х	Х	X	Х	Х			
Efgartigimod PH20 SC ^t	Х	X	Х	Х	Х	Х	Х	Х	Х	Х	Х	Х	Х	Х	Х		
Prednisone taper ^u	Х	X	Х	Х	Х	Х	Х	Х	Х	Х	Х	Х	Х	Х	X		

Trial period		Open-label extension									Follo	ow-up					
Visit number	V1 Roll over ^a	V1 + 4 weeks	V1 + 8 weeks	V1 + 12 weeks	V1 + 16 weeks	V1 + 20 weeks	V1 +24 weeks	V1 + 28 weeks	V1 + 32 weeks	V1 + 36 weeks	V1 + 40 weeks	V1 + 44 weeks	V1 + 48 weeks	V1 +51 weeks EoT/ET	UNS ^b	Safety follow- up 1 EoT/ET + 4 weeks ^c	Safety follow- up 2 EoT/ET + 8 weeks EoS ^c
Assessment/procedure	±0 days						±2 d	ays ^d								±3 days ^d	±3 days ^d
Concomitant therapies/procedures		Continuous monitoring															
AE monitoring								Cor	ntinuou	s monit	oring						

ABQOL=Autoimmune Bullous Disease Quality of Life; AE=adverse events; ALT=alanine aminotransferase; ALP=alkaline phosphatase; AST=aspartate aminotransferase; BMI=body mass index; BUN=blood urea nitrogen; CR=complete clinical remission; CRmin=CR on minimal therapy; CRP=C-reactive protein; DC=disease control; Dsg=desmoglein; ECG=electrocardiogram; EoC=end of consolidation; EoS=end of study; EoT=end of treatment; EQ-5D-5L=EuroQol 5-dimension 5-level scale; ET=early termination; GGT=gamma-glutamyl transferase; GTI=Glucocorticoid Toxicity Index; IgG=immunoglobulin type G; IMP=investigational medicinal product; LDH=lactate dehydrogenase; LDL-C=low-density lipoprotein cholesterol; MCV=mean corpuscular volume; NAb=neutralizing antibody; PDAI=Pemphigus Disease Area Index; PD=pharmacodynamic; PK=pharmacokinetics; QTcF=Fridericia corrected QT interval; rHuPH20=recombinant human hyaluronidase PH20; RBC=red blood cells; SC=subcutaneous(ly); UNS=unscheduled visit; W=week; WBC=white blood cells; V=visit at site

- ^a For participants who roll over from ARGX-113-1904 to ARGX-113-1905, the baseline visit will occur for these participants at the same visit as the EoS/ED visit in study ARGX-113-1904. All assessments will be performed before IMP administration.

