2.3.2. Benefit Assessment

Efgartigimod has been shown to effectively reduce IgG antibodies and improve clinical outcomes in several clinical trials of healthy participants and those with pemphigus, MG, or ITP.

In the phase 2 trial ARGX-113-1701 in participants with pemphigus, the efficacy of efgartigimod is supported by pharmacodynamic effects (effects on IgG and anti-Dsg-1 and -3 autoantibodies) and the effects on the clinical activity (PDAI) and clinical outcomes of the disease (DC and CR). The drug had a fast onset of action by sharply reducing the serum levels of autoantibodies. Autoantibody reduction was correlated with a rapid decrease of the disease activity (PDAI), and was associated with an early achievement of DC and CR. Participants achieved DC with or without concomitant prednisone, while participants achieved CR when efgartigimod administration was combined with low-dose prednisone. Flare was prevented when efgartigimod was given at weekly intervals, before and after DC or CR.

In Dec 2021, the FDA approved efgartigimod for the treatment of generalized myasthenia gravis (gMG) in adult patients who are anti-acetylcholine receptor antibody (AChR-Ab) seropositive. In the phase 2 trial (ARGX-113-1602) of gMG participants, 4 weekly IV infusions of 10 mg/kg efgartigimod led to statistically significant improvements in clinical scales and were well tolerated.¹¹ Additionally, in a randomized, double-blinded, placebo-controlled, phase 3 trial in participants with MG (ARGX-113-1704), the primary endpoint was met: the percentage of AChR-Ab seropositive participants who, after the first treatment cycle, had reduction of \geq 2 points on the Myasthenia Gravis Activities of Daily Living (MG-ADL) total score compared to study entry baseline for \geq 4 consecutive weeks, with the first \geq 2-point reduction observed no later than 1 week after the last IMP infusion. Participants who met this criterion were considered MG-ADL responders. In the AChR-Ab seropositive population, there was a statistically significantly higher proportion of MG-ADL responders in the efgartigimod group (67.7%) than in the placebo group (29.7%) (p<0.001; logistic regression, 2-sided exact p-value) in cycle 1.

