9.5.1. General Considerations

The baseline value for study ARGX-113-1905 will be the value at the last visit in ARGX-113-1904.

All trial visits will be recalculated based on actual dates and will be referred to as "analysis visits" which will be used in the statistical analyses. The rules for calculating the analysis visits will be documented in the SAP. Rules for imputing partial dates or missing dates will also be documented in the SAP.

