#### 2.2.3 Baseline and change from baseline

The baseline value for 1905 will be the value at the Roll-over visit (which corresponds with the last available value of the 1904 study (at the 1904 EoS visit/1905 Roll-over visit)).

Additionally, for PDAI and PD, changes from 1904 baseline will be presented, with 1904 baseline defined as the last available and non-missing value prior to first IMP administration in the 1904 study (detailed definition of 1904 baseline in 1904 SAP).

SGS	Statistical Analysis Plan	
ARGX-113-1905	Final analysis	Final 1.0 of 26APR2024

Change from baseline at time point t is defined as:

value at time point t – baseline value

Percentage change from baseline at time point t is defined as:

100\*([value at time point t – baseline value] / baseline value)

Furthermore, for PDAI, PD, albumin and LDL-C a treatment period-specific baseline (TPnB) will be defined as the last available and non-missing value prior to the first administration of EFG PH20 SC in treatment period n, with n=1, 2, 3, etc....

Assessments on day 1 of a treatment period without time collection or with time information exactly equal to the time of first IMP administration and which are planned predose will be considered as predose.

Change from TPnB at time point t =

value at time point t – TPnB value.

Percent change from TPnB at time point t =

100\*([actual value at time point t - TPnB value]/ TPnB value).

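### SAP 4.3.2 removes an anti-Dsg parameter from actual values when it is BLQ at roll-over, a measurement taken after 1904 treatment, so the displayed roll-over level can be biased upward

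*SAP*

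**What the plan says.** The exclusion is in SAP 4.3.2: "For participants with a baseline value below the limit of quantification (BLQ), the parameter will be excluded in presentation of actual values". The sentence goes on to drop the same participants from change and percent change from baseline, and promises a footnote. It names no visit, so the natural reading is that the parameter disappears from actual values at every 1905 visit.

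What baseline means is settled elsewhere. SAP 2.2.3 says "The baseline value for 1905 will be the value at the Roll-over visit", and Protocol 9.5.1 agrees: "The baseline value for study ARGX-113-1905 will be the value at the last visit in ARGX-113-1904". The two other references have their own names in SAP 2.2.3:

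- 1904 baseline: "with 1904 baseline defined as the last available and non-missing value prior to first IMP administration in the 1904 study".
- Treatment-period baseline (TPnB): "the last available and non-missing value prior to the first administration of EFG PH20 SC in treatment period n".

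SAP 4.3.2 itself lists baseline, 1904 baseline and TPnB side by side, so the unqualified word is the roll-over value.

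The paragraph just before the exclusion, and SAP 2.3.3, both say that anti-Dsg values below the limit are set to that limit. SAP 4.3 presents PD data for the Roll-over set. Table 14.2.3.4, a topline output, shows anti-Dsg actual values together with percent change from each of the three references.

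**The concern.** Of the antecedent study, the Protocol synopsis says "This trial has a treatment period of up to 30 weeks". On the phase 2 pemphigus data, Protocol 2.3.2 says "The drug had a fast onset of action by sharply reducing the serum levels of autoantibodies". A participant can therefore be BLQ at roll-over because treatment lowered the antibody. The rule cannot tell that participant from one who never had the antibody, and it removes both.

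Three consequences follow.

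- **Roll-over visit.** The lowest values are removed from the summary of actual values, so the displayed level is too high.
- **Later visits.** The excluded participants stay out whatever happens to them. If they remain low, the displayed level is too high. If they rise, for example at a flare, the table hides the rise.
- **Mixed populations within one table.** Read literally, the exclusion does not cover change versus 1904 baseline or TPnB, so these participants are in some columns of Table 14.2.3.4 and missing from others.

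Tables are shown by prior treatment. If BLQ shares differ between prior arms, the exclusion also affects the displayed groups unequally.

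**Working it through.** The plan gives no figure to reproduce: no limit of quantification, no expected BLQ share and no hypothesis test. The check has two parts, one on the text and one on direction and possible size.

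**Text**

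1. The roll-over visit is the 1904 end-of-study or early-discontinuation visit, so it follows 1904 treatment.
2. A BLQ result at a later visit, in someone quantifiable at roll-over, is kept at the limit. A BLQ result at roll-over removes the participant from actual values throughout. The same kind of result is handled in two ways.
3. Protocol Table 1, footnote a, says of the roll-over visit "All assessments will be performed before IMP administration"; Table 2 has an equivalent footnote. For participants dosed at roll-over, the TPnB for period 1 is therefore the roll-over value. Change from roll-over and change from that TPnB are then the same number, yet on the literal wording one is excluded and the other kept.

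**Roll-over mean.** Let *s* be the share of pre-treatment-quantifiable participants who are BLQ at roll-over (assumed 10–30%), and *k* the retained participants' mean in multiples of the limit (assumed 3–10). With BLQ values set to the limit, the mean is (1−s)k + s. With them excluded it is k. The ratio of displayed mean to full mean is k / ((1−s)k + s).

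| s | k = 3 | k = 10 |
|---|---|---|
| 10% | 3/2.8 = 1.071 | 10/9.1 = 1.099 |
| 20% | 3/2.6 = 1.154 | 10/8.2 = 1.220 |
| 30% | 3/2.4 = 1.250 | 10/7.3 = 1.370 |

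**Roll-over median and first quartile.** Every BLQ value lies below every retained value, so no assumption on *k* is needed. The displayed median is the s + (1−s)/2 quantile of the full distribution, and the displayed Q1 is the s + (1−s)/4 quantile.

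| s | Displayed median is really the | Displayed Q1 is really the |
|---|---|---|
| 10% | 55th percentile | 32.5th percentile |
| 20% | 60th percentile | 40th percentile |
| 30% | 65th percentile | 47.5th percentile |

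**Later visits.** Let *r* be the excluded participants' mean divided by the retained participants' mean. The ratio is 1 / ((1−s) + s·r).

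| s | r = 0.5 | r = 1 | r = 1.5 |
|---|---|---|---|
| 10% | 1.053 | 1.000 | 0.952 |
| 20% | 1.111 | 1.000 | 0.909 |
| 30% | 1.176 | 1.000 | 0.870 |

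The sign reverses once the excluded group's mean exceeds the retained group's.

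**Cross-check by a different route.** With lognormal roll-over values (log-SD 1.0 to 2.0, assumed), closed-form moments give a mean ratio of 1.09–1.11 at 10% BLQ and 1.28–1.41 at 30%. The median ratio is 1.13–1.29 and 1.47–2.16 respectively. The direction is upward in every scenario.

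The formulas ignore participants who were BLQ before treatment but quantifiable at roll-over.

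**The case against.** The strongest defence is that the rule has a sensible purpose. Protocol 2.2 describes PF as anti-Dsg-3 negative, and SAP 3.2.1 classifies participants by which antibody they carry. Dropping a parameter a participant never had stops such participants from pulling the summary towards the limit. That purpose is legitimate, but a roll-over value cannot serve it. The 1904 baseline can, and these tables already use it.

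Second, nothing in the documents shows that many participants fall below the limit. A sharp reduction is not the same as BLQ. The 65% maximum mean reduction in Protocol 2.3.2 is for total IgG in ITP. If anti-Dsg fell by the same fraction (an assumption), only pre-treatment values under 1/(1 − 0.65) ≈ 2.9 times the limit would become BLQ. Some participants also had placebo, stopped drug at CRmin or rolled over early. This stands as a limit on size: the frequency is unknown and may be low. It does not change the direction at roll-over.

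Third, the SAP does not say which baseline governs the by-period display. If it were read as each column's own reference, the conflict between change from roll-over and change from TPnB would disappear. That part is fairly called an ambiguity. The treatment of actual values does not depend on it.

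Fourth, the exclusion is footnoted, n is reported and all values are listed. This discloses the selection but leaves the summary selected.

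**Conclusion.** The concern holds. As written, the rule selects the anti-Dsg display on a possible treatment result. The upward direction at roll-over is arithmetic once any pre-treatment-quantifiable participant is BLQ there; at later visits it is likely but not assured. The illustrative overstatement of the roll-over mean is 7–37% for assumed BLQ shares of 10–30% and a retained mean of 3–10 times the limit. The actual size cannot be derived from the documents.

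Importance is minor. The endpoint is secondary and descriptive, no hypothesis is tested, and the primary safety analysis is untouched. Read literally, percent change from 1904 baseline in the same table keeps these participants, so the reduction from pre-treatment is still shown with them included. The sponsor should still correct the rule, because it affects a topline table.

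**What to change.** Amend SAP 4.3.2 as follows.

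1. Keep participants who are BLQ at roll-over in anti-Dsg actual values at the lower limit, as 4.3.2 and 2.3.3 already provide for BLQ values. Use one term for that limit; 2.3.3 calls it the detection limit and 4.3.2 the limit of quantification.
2. If participants without measurable antibody are to be screened out, define them by a BLQ 1904 baseline for that antibody and apply the screen to every column of Tables 14.2.3.3 and 14.2.3.4. Without this step, item 1 also adds never-positive participants at the limit, which lowers anti-Dsg-3 summaries in particular.
3. Report the number and percentage BLQ by visit and prior arm.
4. Change and percent change from roll-over may still exclude participants who are BLQ at roll-over, because a censored reference leaves a one-sided floor. Apply the same rule to change from TPnB when that TPnB is BLQ, and footnote the resulting difference in n.

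The exclusion sentence speaks of the parameter in general, so the SAP should also state whether it is meant to reach total IgG and its subtypes.

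The cost is SAP wording, one count row per visit and one footnote. Actual values and change from roll-over will no longer share one n if item 4 is used, and setting BLQ values to the limit slightly overstates the lowest levels.

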### 4.3.3 Presentation of results

All PD endpoints will be summarized by means of descriptive statistics at each analysis visit. Tables will present:

- a) Actual values, changes from baseline and percent changes from baseline by analysis visits overall.
- b) Changes and percent changes versus 1904 baseline by analysis visits overall.
- c) Actual values, changes from TPnB and percent changes from TPnB by analysis visits by period/subperiod.
- d) Changes and percent changes versus 1904 baseline by analysis visits by period/subperiod.

#### 4.4 **IMMUNOGENICITY**

Immunogenicity data will be presented for the Safety analysis set.

#### 4.4.1 Available data

Blood samples will be collected for the determination of anti-drug antibodies (ADA) to efgartigimod (in serum samples) and antibodies against rHuPH20 (in plasma samples, only analyzed in case of safety concerns and not in scope of this analysis) at the time points indicated in the schedule of activities (see section 9.2).

SGS	Statistical Analysis Plan	
ARGX-113-1905	Final analysis	Final 1.0 of 26APR2024

[figure not shown]
Immunogenicity samples are analyzed in a 3-tiered approach:

[figure not shown]
- All samples are evaluated in the ADA screening assay and are scored ADA screening positive or negative.
- If a sample scored positive in the ADA screening assay, it is further evaluated in the confirmatory assay and is scored confirmed positive (positive immunodepletion) or confirmed negative (negative immunodepletion).
- If a sample is scored as confirmed positive, the samples are further characterized in the ADA titration assay (to determine titer) and are also further analyzed in the NAb assay to confirm neutralizing activity. For NAb against efgartigimod, a screening assay is performed and results will be reported as negative or positive.

If available, a titer result will be reported for the ADA confirmed positive samples. However, a titer result is not always available:

- In case the ADA confirmed positive sample could not be run in the titration assay (e.g. due to insufficient sample volume/quality to perform the titer analysis), the result will be described as 'positive immuno-depletion' and the sample should be considered as ADA positive.
- If a sample is negative in the titration assay, it will be reported as 'negative titer' but it should be considered as ADA positive since it was confirmed positive in the second tier.
- If a sample could not be analyzed or reported as 'positive screen', the ADA sample status is ADA unevaluable

[figure not shown]
An overview of this 3-tiered approach and all possible ADA sample results that will be reported by the laboratory is presented in Figure 1. From these reported ADA sample results a final ADA sample status needs to be derived during the statistical analysis, as presented in the final column ('Final ADA Outcome'):

- a missing screen includes the following terms (reported as reason not done): NA (not analyzed), NR (no result), NS (no sample) and SL (sample lost). More details can be found in the IS data transfer agreement (DTA) from LGC (for ADA against efgartigized) with SGS SDO.
- b 'positive titer' is reported in case it was not possible to retrieve a numeric value.

Page 45 of 84

#### 4.4.2 Derivation rules

#### 4.4.2.1 PARTICIPANT CLASSIFICATION FOR ADA AGAINST EFGARTIGIMOD-OVERALL

Table 6 below gives an overview of how the ADA participant classification will be derived, starting from the participant baseline ADA sample status.

Participant	Highest c post-baseline d sample status				
ADA classification	ADA negative	ADA positive (missing titer a )	ADA positiv titer b or posi numeric ti	itive titer or	ADA not evaluable
Baseline ADA sample status					
ADA negative	ADA negative	Treatment- Induced ADA	Treatment-In	nduced ADA	ADA unevaluable
ADA positive (missing titer a )	Treatment- Unaffected ADA	ADA unevaluable	ADA une	waluable	ADA unevaluable
ADA positive (negative titer b or positive titer or numeric titer value)	Treatment- Unaffected ADA	ADA unevaluable	titer < 4 x baseline titer: Treatment- Unaffected ADA	titer ≥ 4x baseline titer: Treatment- Boosted ADA	ADA unevaluable
ADA not evaluable	ADA unevaluable	ADA unevaluable	ADA une	waluable	ADA unevaluable

Table 6: Participant classification for ADA against Efgartigimod

a Samples with missing titer have as reported ADA result 'positive immunodepletion'or 'positive titer';

b Results reported as 'negative titer', i.e. titer value <1 will be set to value of 1;

c Highest sample status, with order: (from low to high): ADA unevaluable, ADA negative, ADA positive (missing titer /positive immunodepletion), ADA positive with titer <= 1 ('negative titer' as reported ADA result, titer value set to 1), ADA positive with titer >1 (i.e. numeric titer and selecting the sample with highest titer)

d For the overall ADA participant classification, the highest post baseline sample status is used for comparison with the baseline ADA sample status.

ADA evaluable participant = participant classified as any of following categories: ADA negative, treatment-unaffected ADA, treatment-induced ADA, treatmentboosted ADA. The first 2 categories are classified as 'ADA negative', the latter 2 as 'ADA positive'.

ADA unevaluable participant = participant classified as ADA unevaluable or with missing baseline ADA sample or without post-baseline ADA samples.

Note: Fourfold difference in titer values is considered significant in case a twofold serial dilution is applied (= 2 times the dilution factor) (reference to Shankar et al., 2014).

ADA incidence = percentage of participants with treatment-induced or treatmentboosted ADAs (denominator: number of evaluable participants).

SGS	Statistical Analysis Plan	
ARGX-113-1905	Final analysis	Final 1.0 of 26APR2024

ADA prevalence = percentage of participants with treatment-unaffected ADA, treatment-induced ADA or treatment-boosted ADA (denominator: number of evaluable participants).

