ARGX-113-1905 provides efgartigimod PH20 SC extended treatment and retreatment options for participants who were randomized to the efgartigimod PH20 SC treatment arm in ARGX-113-1904, and provides first efgartigimod PH20 SC treatment and retreatment options for participants who were randomized to the placebo treatment arm in ARGX-113-1904.

At blinded rollover from ARGX-113-1904 into ARGX-113-1905, participants may be in different clinical stages: participants may have achieved CRmin; participants may have achieved

CR without meeting the minimal therapy criterion; participants may have achieved DC or EoC (the time at which no new lesions have developed for a minimum of 2 weeks and approximately 80% of lesions have healed) without having achieved CR; participants may have had treatment failure or a flare after having achieved CRmin.

ARGX-113-1905 evaluates the ability to (further) taper prednisone therapy and achieve CRoff (CRoff defined as the absence of new and established lesions completely healed while the participant is receiving no prednisone therapy for at least 2 months [8 weeks]), the ability to achieve CR and CRmin for participants who had not yet achieved CRmin, and the ability to treat flare; and assesses participant outcome measures and the safety, PD, PK, and immunogenicity of efgartigimod PH20 SC over the duration of the trial.

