9.5.6. Secondary Endpoints

All secondary endpoints will be presented with descriptive summary statistics. All data collected will be listed, together with derived variables. Graphical displays will show efficacy variables over time.

Descriptive statistical methods will be used to analyze all secondary efficacy data. In addition, summaries for certain subgroups if defined will also be presented. For time to event endpoints, survival curves will be estimated using the Kaplan-Meier time to event method. Summary statistics and summary plots will be presented for all other endpoints including other endpoints including CWS and AIS (as components of C-GTI) and the complementary GTI-SL, QoL, PK, PD, immunogenicity, and self-administration. More details for the analysis of the endpoints will be described in the SAP.

Analyses will not only refer to the baseline of ARGX-113-1905, but the baseline of ARGX1131904 will be used for specific analysis as stated in the SAP for this OLE trial.

More detailed descriptions will be presented in the SAP of the study.

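### ADA incidence in 1905 is measured against the roll-over sample, so in the prior-efgartigimod arm antibody induced in 1904 that does not rise 4-fold is labelled 'treatment-unaffected', grouped as ADA negative and left out of incidence

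*SAP*

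**What the plan says.** SAP 2.2.3 sets one baseline for the extension: "The baseline value for 1905 will be the value at the Roll-over visit", which is the last available 1904 value. It brings in the earlier, pre-dose baseline for two kinds of data only: "Additionally, for PDAI and PD, changes from 1904 baseline will be presented". SAP 4.4 names no other baseline for immunogenicity.

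SAP 4.4.2.1 builds the participant classification "starting from the participant baseline ADA sample status" and compares it with the highest post-baseline status (Table 6). A participant positive at baseline is treatment-unaffected if later samples are negative, or if both titers are known and the rise is below 4-fold. A rise of at least 4-fold is treatment-boosted. A missing titer at either end, with a positive post-baseline sample, is unevaluable. The text then groups the categories ("The first 2 categories are classified as 'ADA negative', the latter 2 as 'ADA positive"), the first two being ADA negative and treatment-unaffected.

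ADA incidence is the "percentage of participants with treatment-induced or treatmentboosted ADAs". ADA prevalence adds the treatment-unaffected category.

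On exposure before roll-over, the protocol synopsis says of 1904: "This trial has a treatment period of up to 30 weeks". Protocol 2.1 says that 1905 offers "extended treatment and retreatment options for participants who were randomized to the efgartigimod PH20 SC treatment arm". Protocol 9.5.6 leaves further use of the earlier baseline to the SAP: "the baseline of ARGX1131904 will be used for specific analysis as stated in the SAP for this OLE trial".

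**The concern.** The word 'unaffected' makes sense only if the baseline sample precedes the drug. It does for the 1904 placebo arm. It does not for the 1904 efgartigimod arm, where a positive roll-over sample may itself be the response to treatment. The same category name then carries two meanings: antibody present before any efgartigimod in one column, and possibly drug-induced antibody in the other. The Total column adds them together.

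Incidence and prevalence of ADA against efgartigimod together form a named secondary endpoint (protocol section 3). SAP 2.1.2 analyses non-efficacy endpoints by the treatment actually received in both trials, and SAP 2.4.2 sets out the columns by prior arm plus a total. The columns therefore reflect exposure over two trials while the ADA baseline reflects only the second. A reader comparing incidence between columns would be comparing different quantities. The participants concerned are those with the longest exposure.

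**Working it through.** The plan states no figure to reproduce, so the check is to apply the Table 6 rules to one type of participant under two baselines.

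**Inputs.** The rules come from SAP 4.4.2.1 and the baseline from SAP 2.2.3. Assumed participant: ADA negative before 1904 dosing, made positive by efgartigimod in 1904, roll-over titer 8 (an arbitrary value). The boosting threshold is 4 × 8 = 32.

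| Highest 1905 result | Against roll-over sample (SAP) | Two-level group | Against 1904 pre-dose sample, 1905 samples only |
|---|---|---|---|
| Negative | Unaffected | ADA negative | ADA negative |
| Titer 4, 8, 16 or 31 | Unaffected | ADA negative | Induced |
| Titer 32 or 64 | Boosted | ADA positive | Induced |
| Positive, titer missing | Unevaluable | none | Induced |
| Not evaluable | Unevaluable | none | Unevaluable |

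If the roll-over sample is itself counted as post-baseline, as a classification over both trials would do, every row in the last column becomes treatment-induced.

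If the roll-over sample is positive but has no titer, the rules give unaffected when all later samples are negative and unevaluable when any is positive.

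**Effect on the percentages.** Take 100 evaluable participants of the prior-efgartigimod arm. Let q be the number induced in 1904 and persisting with less than a 4-fold rise, and r the number newly induced in 1905. Assume no antibody before 1904 dosing and no boosted cases.

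- SAP incidence = r/100
- SAP prevalence = (q + r)/100
- Incidence against the 1904 pre-dose sample, 1905 samples only = (q + r)/100

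The shortfall in incidence is q/100. The documents give neither q nor r. To show the arithmetic only:

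- q = 5, r = 2: incidence 2%, prevalence 7%
- q = 20, r = 5: incidence 5%, prevalence 25%

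**Coherence with NAb.** SAP 4.4.2.2 sends only confirmed ADA positives to the NAb assay. Its NAb incidence counts participants positive both at baseline and afterwards, whereas ADA incidence omits the corresponding unaffected participants. Suppose, per 100 evaluable for both, 7 persist from 1904, 3 are new, and 4 of the 7 are NAb positive at roll-over and later. ADA incidence is then 3% and NAb incidence at least 4%. The subset would show a higher incidence than the set it is drawn from.

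**The case against.** The strongest defence has four parts.

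**The information is still in the outputs.** This stands. Prevalence counts these participants. SAP 4.4.3 tabulates each participant category and baseline sample status, and tables are shown by prior arm. The NAb cross-tabulation lists treatment-unaffected and ADA negative as separate categories. No output in SAP 4.4.3 or section 8 is expressly specified on the two-level grouping, and none of the listed efficacy, PK or safety tables is split by ADA status. A reader might infer that drug-induced ADA vanish from the report. The documents do not support that.

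**The baseline follows the protocol.** This also stands. Protocol 9.5.1 fixes the baseline as the last 1904 visit, and 9.5.6 makes use of the earlier baseline optional. Incidence arising in 1905 is a legitimate quantity for an extension trial. What it does not justify is calling previously exposed positives unaffected or negative.

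**No size can be given.** This stands. One could multiply an assumed 5–20% induced in 1904 by an assumed 50–90% persisting, giving 0.05 × 0.50 = 2.5% to 0.20 × 0.90 = 18%, and read that as the share misclassified. That inference fails for several reasons:

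- Both inputs are assumptions.
- Rises of at least 4-fold are counted as positive, and some missing-titer cases become unevaluable.
- Immunogenicity uses the Safety set (SAP 2.1.1 and 4.4), so those who entered in CRmin and were never dosed in 1905 are excluded.
- Thirty weeks is a maximum, because 1904 dosing stopped at CRmin.

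**NAb incidence is not affected in the same way.** Correct. It already includes persistent positives, so the point does not extend to it.

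**Conclusion.** The point holds within narrow limits. In the prior-efgartigimod arm, ADA induced in 1904, present with a titer at roll-over, and then negative or rising less than 4-fold are labelled treatment-unaffected, grouped as ADA negative and left out of ADA incidence. The label has a different meaning in the prior-placebo arm, so incidence and the unaffected category cannot be compared between the two columns or read from the Total.

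The conclusion rests on the SAP's own rules and on one fact, that the roll-over sample in this arm follows efgartigimod exposure. It does not depend on any assumed rate. Its numerical size is unknown and should not be quoted. Participants negative at roll-over are not touched by the misclassification. The primary safety endpoints are unaffected, and prevalence remains correct as defined.

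**What to change.** 1. Keep the roll-over baseline as a 1905-only view and name it as such. Label incidence 'new or boosted in 1905'. In the prior-efgartigimod arm, label roll-over positives 'positive at roll-over (previously exposed)', show them by prior arm, and do not group them under ADA negative.
2. If 1904 pre-first-dose ADA results are available and the assay is comparable, add a supplementary classification of the prior-efgartigimod arm against that sample over 1904 and 1905 together. The SAP already uses the 1904 baseline for PD. The two documents do not show that such ADA results exist, so the sponsor has to confirm this first.

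The first change costs SAP wording and table programming. The second adds one table and a merge of 1904 results, with no new samples if those results exist. Its small downside is a second observation window, which must be labelled and not pooled in the Total column.
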